### **6.9.5 Route of Administration**

BUP will be administered sublingually.

### **6.9.6 Starting Dose and Dose Escalation Schedule**

The starting dose and dose escalation schedule will be uniform among study participants during the index visit of the study. The regimen will vary only on timing of dosage administration, which will be determined based on each individual participant's withdrawal symptoms using various scales. After the Day 3 visit or if a participant has objective signs of withdrawal, a prescription for 16 mg BUP may be given to last until the participant's follow-up care appointment. Continued treatment and appropriate dosage of BUP-NX for each participant will be determined by the OUD-experienced provider they are referred to, and will be a joint decision between the study participant and provider.

### **6.9.7 Dose Adjustments/Modifications/Delays**

All study participants will receive the 32 mg loading dose of BUP at the index visit. Thereafter, dose adjustments can be made on an individual basis, i.e. maintenance dosing of BUP can be escalated if withdrawal and craving are prevalent, or can be reduced if over sedation is a concern. Study assessments (see Section 7.1) will help the provider determine the course of action.

### **6.9.8 Duration of Therapy**

This study aims to pilot a novel induction strategy for long term treatment of OUD with BUP. As part of the

Study Number: s19-01700

Version: 7.0

Version Date: 08/01/2022

study, participants will be monitored for one month after induction, but the goal is to facilitate continuation of treatment beyond this study; referral to continued treatment will be provided if desired.

### **6.9.9 Tracking of Dose**

On days 1 – 3, following the index visit, participants will participate in in-person research visits and complete various assessments which will include objective and subjective measures of withdrawal and craving, and side effects. Participants will follow-up by phone at one month and again be asked to report adherence, as well as other substance use (Details of assessments can be found in Sections 7.1 and 7.3).

### **6.9.10 Study Agent Accountability Procedures**

See Section 6.9.6. The initial 32mg loading dose of BUP will be dispensed from the Bellevue Hospital ED medication dispensing system and administered by a member of the research team in conjunction with the treating clinician. Participants will be given a prescription for BUP-NX (16mg daily in 8mg tablets/films) to last between their third research visit and their appointment for continuing treatment.

## **7 Study Procedures and Schedule**

### **7.1 Study Specific Procedures**

#### *Baseline Measures*

At baseline, socio-demographic information will be collected including age, sex, race/ethnicity, and housing status.. A broad range of tools selected from the Study Measures will be assessed at baseline and repeated at subsequent visits, include measures of substance use, opioid withdrawal and craving, risk behaviors, and quality of life. A urine pregnancy test will be used to confirm study eligibility among females of childbearing potential unless one has been performed already clinically. A urine and/or saliva toxicology test (standard drug panel plus BUP and fentanyl) will be collected for research-only purposes. No study-related activities will be performed prior to obtaining written informed consent.

#### *Outcome measures*

Engagement in treatment will be assessed by self-report and verified by contact with the participant's provider after the 30 day follow up visit. Tools selected from the Study Measures will also be used to assess substance use, functional outcome, opioid withdrawal and craving, general health, quality of life, and treatment preference.

### **7.2 Standard of Care Study Procedures**

As part of standard clinical care, patients in opioid withdrawal will have a basic history and physical examination completed, including many of the assessments we will complete as study measures (e.g., drug use screening, DSM5, COWS). The provider may choose to obtain basic bloodwork and/or urine testing as indicated by clinical signs and symptoms or in anticipation of treatment. This includes, but is not limited to, a pregnancy test. Toxicology tests are not routinely obtained clinically in the ED primarily because the available tests are not capable of detecting fentanyl (or most other synthetic opioids) and because there are reliable, objective clinical signs and symptoms of opioid intoxication and withdrawal. It would be considered unethical to require toxicology testing to demonstrate the presence of opioid use in order for a patient to receive life-saving treatment (i.e., BUP) when the test itself cannot detect one of the most prevalent opioids being used. As such, toxicology testing in the ED is of little utility.

Whether they consent to study participation or not, all patients who present in clinical opioid withdrawal can receive symptomatic treatment for withdrawal. If an X-waivered provider is available in the ED, the patient will be able to receive BUP according to that provider's usual clinical practice. Patients with OUD can also receive referral for outpatient treatment and follow-up, as clinic availability allows

### **7.3 Laboratory Procedures/Evaluations**

#### **7.3.1 Clinical Laboratory Evaluations**

See section 7.1 and 7.2 for laboratory evaluation that may be done as part of standard of clinical care or study procedures.

## **7.4 Study Schedule**

### **7.4.1 Screening**

### **7.4.2 Enrollment/Baseline**

#### **Index ED Visit (Day 0, 4 – 8 hours)**

- Perform baseline assessments:
  - Obtain demographic information, medical/psychiatric history, medication history, substance use history.
  - Obtain informed consent of potential participant verified by signature on written informed consent for screening form.
  - Perform medical examinations needed to determine eligibility based on inclusion/exclusion criteria.
  - Review history and verify inclusion/exclusion criteria.
  - Collect urine or saliva samples for toxicology testing, collect urine for a pregnancy test (in females of childbearing potential, if not performed clinically).
  - Assess and quantitate opioid and other substance use, withdrawal, craving, motivation for treatment, health status questionnaire, health services utilization).
- Participants receive total 32mg BUP in divided doses. After the participant has received a total of 8mg, participants will be observed for 30 minutes to ensure that there are no adverse reactions to BUP-NX. If the participant has a qualifying adverse event after the first dose (e.g., allergic reaction or other clinically significant AEs as described in Section 5.1.1), the second dose will not be given and the participant will be withdrawn from the study without receiving subsequent doses. Otherwise, the second dose of 24 mg will be administered.
- Participants will be assessed using opioid withdrawal scales (COWS, SOWS, VAS) prior to BUP administration and every 30 minutes afterward for at least 90 minutes after last dose.
- Participants will be discharged with 4 scheduled appointments, 3 research visits (days 1, 2, 3), an appointment for follow up with a BUP provider for ongoing OUD treatment, and a research follow-up phone call on Day 30, which marks the end of the study for the participant.
- In light of the health safety risks associated with the COVID-19 pandemic, interviews may be conducted remotely, rather than in-person, using an approved, secure audio or audio-video connection (e.g., telephone, Cisco Webex) from a setting offering adequate privacy. Participants will be advised that they may disconnect their video feed.

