Active use of opioids (within 7 days) will be confirmed by a positive toxicology test and/or by the clinical assessment by the study clinician or ED provider (e.g., self-report plus documented history of opioid use and objective findings consistent with opioid withdrawal). We will not rely on toxicology testing alone as synthetic and semi-synthetic opioids are not reliably detected for up to 7 days using currently available CLIA-waived, rapid toxicology tests. The use of urine and/or saliva toxicology tests that are not CLIA-waived will be for non-clinical, research purposes.

Participants will receive the BUP SL 32mg in divided doses, rather than all at once. If after an initial dose of BUP  $\leq$  8mg SL, a participant experiences over-sedation or another adverse event that would preclude further dosing, such as an allergic reaction, the subsequent dose will not be administered and the patient will be withdrawn from the study. The participant will be reassessed for other possible etiologies for these symptoms (for example, infection can cause sedation or mimic withdrawal). Precipitated withdrawal, however, would not necessarily preclude subsequent BUP dosing. In most cases, the treatment for precipitated withdrawal is to administer additional BUP in higher doses. In other words, the latter BUP 24mg dose would be the treatment for precipitated withdrawal in most cases. The determination of whether a participant who is experiencing apparent precipitated withdrawal should receive additional BUP will be determined on a case-by-case basis at the discretion of the study clinician.

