## 5 Study Endpoints

### 5.1.1 Primary Study Endpoints

#### 1. To estimate the proportion having “*successful rapid induction*”

*Successful Rapid Induction*, the primary study endpoint, is defined as completing rapid induction with a loading dose of BUP SL 32mg without experiencing a clinically significant serious and/or severe adverse event (AE) related to the intervention – specifically, the receipt of a dose of BUP SL greater than 8mg during the Index ED visit. We will determine the proportion of participants who have successful rapid induction during the ED index visit amongst all study participants.

- *Clinically significant adverse events* (AEs) include the following: over-sedation (defined as requiring invasive or non-invasive ventilator support, having a Richmond Agitation-Sedation Scale (RASS) of  $\leq -3$ , and/or clinician determination), hemodynamic instability (e.g., persistent hypotension not attributed to other causes), development of severe precipitated withdrawal

Study Number: s19-01700

Version: 7.0

Version Date: 08/01/2022

(clinician determination), or experiencing other unexpected, SAEs, related to receipt of the second dose of BUP SL (for a total of BUP SL 32mg) as defined in *Section 8.1*. This measure will be assessed at the end of the ED index visit.

- Precipitated withdrawal: Clinicians will assess whether an event is considered precipitated withdrawal. This clinical determination will be based on the severity of the withdrawal signs and symptoms, the rapidity of the onset of withdrawal symptoms, and clinical factors (e.g. timing since last use of an opioid agonist(s), type(s) of opioid agonist, duration of action of opioid agonist(s) used, and route of administration). Scores will be based on objective components, eliminating nausea which can be a side effect of BUP administration. Patients who experience precipitated withdrawal will be treated with ancillary medications.

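### Severe precipitated withdrawal after the first 8 mg: Section 7.4.2 requires withholding the 24 mg and withdrawing the participant, while Section 2.1.4 leaves the 24 mg to the study clinician

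*Combined protocol and SAP*

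**What the plan says.** **Section 7.4.2 (index visit).** After 8 mg in total there is a 30-minute observation. If a qualifying adverse event follows the first dose, the examples given being an allergic reaction or "other clinically significant AEs as described in Section 5.1.1), the second dose will not be given and the participant will be withdrawn". In all other cases the 24 mg is given.

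**Section 5.1.1 (primary endpoint).** The list of clinically significant adverse events that Section 7.4.2 points to includes "development of severe precipitated withdrawal", by clinician determination. It ends with other unexpected serious events "related to receipt of the second dose of BUP SL". The same section adds: "Patients who experience precipitated withdrawal will be treated with ancillary medications". On the analysis it says: "We will determine the proportion of participants who have successful rapid induction during the ED index visit amongst all study participants".

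**Section 2.1.4 (medication risks).** Over-sedation, or another event that rules out further dosing, leads to withholding and withdrawal. There is then an exemption: "Precipitated withdrawal, however, would not necessarily preclude subsequent BUP dosing". It continues that "the latter BUP 24mg dose would be the treatment for precipitated withdrawal in most cases", and that whether to give more buprenorphine "will be determined on a case-by-case basis at the discretion of the study clinician".

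**Other wordings of the same step.** Section 6.9.4 gives the 24 mg unless there is an unexpected significant adverse event. Section 6.7.1 says the investigator may, rather than will, end participation. Section 2.1.6 refers back to the medication-risk text for discontinuing medication.

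**The concern.** For severe precipitated withdrawal after the first dose, one section removes a discretion that another grants. The 24 mg is the only part of the regimen under evaluation, since Section 6.7.1 describes the initial 8 mg as standard ED dosing. Precipitated withdrawal is one of the two medication risks singled out in Section 2.1.4. Enrolment runs across several EDs (Section 6.6), so divergent handling is a practical possibility.

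There is also a consequence for the estimate. Success requires the full 32 mg (Section 3.1). A participant held at 8 mg cannot succeed, even on the looser gloss in Section 5.1.1 that the dose received exceed 8 mg. A participant given the 24 mg still can. The choice of rule therefore feeds directly into the primary proportion.

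**Working it through.** The plan gives no figure on this point, so the check is mainly a comparison of texts.

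**1. The rules side by side, for events after the first 8 mg**

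| Event | Section 7.4.2 with the 5.1.1 list | Section 2.1.4 |
|---|---|---|
| Severe precipitated withdrawal | 24 mg withheld, participant withdrawn; mandatory | Clinician's discretion; 24 mg is the usual treatment |
| Non-severe precipitated withdrawal | Not on the list, so the 24 mg is given by default | Clinician's discretion; 24 mg is the usual treatment |
| Over-sedation | Withheld and withdrawn | Withheld and withdrawn |

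The conflict lies in the first row. The non-severe row shows no comparable clash, because what one section directs the other allows and calls usual.

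**2. Can the texts be read together?**

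- The phrase in Section 5.1.1 tying events to the second dose attaches most naturally to the last item, other unexpected serious events. If it covered the whole list, the cross-reference in Section 7.4.2 to that list for first-dose events would have nothing to apply to.
- Section 7.4.2 introduces the list by way of example, but the 5.1.1 events are the named examples, so this creates no exception.
- Clinician determination in Section 5.1.1 concerns whether the event is severe precipitated withdrawal, not whether to dose once it has been so judged.
- Section 6.9.4 does not settle the matter. Precipitated withdrawal is a described risk, which points towards dosing, but Section 8.2.3 lets an event be unexpected by its severity.

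**3. Effect on the primary proportion**

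Inputs: 35 participants (Section 6.6). Assumptions: exactly one participant has the event and every other participant succeeds, as Section 3.1 hypothesises. The documents give no rate of severe events after 8 mg, so no event count is projected.

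Exact (Clopper-Pearson) 95% limits for x successes in n: lower = Beta quantile 0.025 with parameters (x, n − x + 1); upper = Beta quantile 0.975 with parameters (x + 1, n − x). When x = n, the lower limit is 0.025^(1/n) and the upper limit is 1.

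- Held at 8 mg and kept as a failure among all participants (Section 5.1.1): 34/35 = 97.1%; Beta(34, 2) and Beta(35, 1) give 85.1 to 99.9.
- Held at 8 mg and excluded because Section 3.1 counts those who receive 32 mg: 34/34 = 100%; lower limit 0.025^(1/34) = 89.7%.
- Held at 8 mg and replaced (Section 6.7.2 continues enrolment to 35), or given the 24 mg with no event counted as related: 35/35 = 100%; lower limit 0.025^(1/35) = 90.0%.

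Each further participant kept as a failure lowers the estimate by 1/35 = 2.9 percentage points. Two would give 33/35 = 94.3% (80.8 to 99.3).

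**The case against.** The strongest reply is that Section 2.1.4 is the only text written specifically for precipitated withdrawal before the second dose. Section 7.4.2 reaches the event only through a general pointer to an endpoint definition, and Section 2.1.6 sends the reader to the medication-risk text. On that view the specific passage governs. Its hedged wording also leaves room to withhold in severe cases, so a clinician could satisfy both sections by choosing to withhold.

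This does not remove the conflict. No precedence rule is stated, and the pointer in Section 2.1.6 only restates one side. That one use of the discretion happens to agree with Section 7.4.2 does not reconcile a discretion with a prohibition.

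Several narrower objections do stand:

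- Study withdrawal is not shown to bar clinical treatment. Section 6.7.2 provides for continued care, and Section 2.1.4 says the Bellevue ED clinical protocol already allows up to the study dose for worsening withdrawal.
- Section 6.7.1 attributes reactions to the first 8 mg to standard dosing. That could make a success of someone who goes on to receive the 24 mg, but not of someone who never receives it.
- The percentages arise through a separate inconsistency over denominator and replacement (Sections 3.1, 5.1.1 and 6.7.2).
- Ancillary medication does not exclude further buprenorphine, so that sentence is incomplete rather than contradictory. The may/will difference and the word unexpected in Section 6.9.4 are minor.

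**Conclusion.** The concern holds. For severe precipitated withdrawal after the first 8 mg, Sections 7.4.2 and 5.1.1 together make withholding and withdrawal mandatory, while Section 2.1.4 makes the decision discretionary and describes giving the 24 mg as usual. This review takes no view on which rule is clinically right.

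With one affected participant and all others succeeding, the reported result lies between 97.1% and 100%, with lower confidence limits from 85.1% to 90.0%. Section 10.1 makes the analysis descriptive with no success threshold, so no formal decision depends on the difference. It does bear on the Section 3.1 hypothesis that all participants succeed, which a single counted failure contradicts. The point should be fixed chiefly because it is a safety-relevant contradiction at the central dosing step, and secondly because it affects who counts as a success.

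**What to change.** Reconcile Sections 2.1.4, 2.1.6, 5.1.1, 6.7.1, 6.9.4 and 7.4.2 into one rule for the second dose, stated once and cross-referenced elsewhere. The rule should cover:

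- severe and non-severe precipitated withdrawal, including how ancillary medication relates to further buprenorphine;
- over-sedation;
- whether withdrawal from the study is mandatory or discretionary.

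The clinical content is for the investigators and the DSMB to decide.

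For the analysis:

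- Record for each participant why the 24 mg was given or withheld.
- Keep eligible enrolled participants who reached the 8 mg step but did not receive the 24 mg in the all-participants denominator that Section 5.1.1 already states.
- Do not count post-enrolment screen failures (Section 6.4) as induction failures.
- Report replacements made under Section 6.7.2 separately.

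The cost is a protocol wording amendment and one CRF field, with no change to sample size or visits. The reported success proportion may be less favourable.

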decline to answer these questions, the PI will advise them that they will not be able to participate and will make a referral to other treatment if interested. All studies involving substance use, including this one, will apply for the added protection of a Federal Certificate of Confidentiality that encompasses protocol activity and participant data and ensure against the release of confidential information. The PI and any future staff will have completed requisite IRB Human Subjects and HIPAA trainings. The PI will provide any future staff with training in their responsibilities for maintaining participant confidentiality; we will use unique identifiers to identify participants in the database; all data will be kept in locked filing cabinets in my locked research office or on our secure server to which only the study team will have access. Study findings will utilize only aggregate data and no publication or presentation will involve any use of individual information.

The study clinician will evaluate all pertinent screening and baseline assessments prior to participant randomization to ensure that the participant is eligible and safe to enter the study. Adverse events (AEs) will be assessed and documented at each visit and during phone check-ins. Individuals who experience an AE that compromises safe participation will be discontinued from further medication administration (as described in medication risks) and provided referrals for other treatment or to specialized care.

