#### 2. To evaluate the safety of rapid induction:

Adverse events will be assessed using an adverse events checklist to be completed at the conclusion of the index visit and at each study visit. Physiologic measure (vital signs) and objective measures of level of awareness (agitation-sedation) will be repeatedly assessed during the index visit (as discussed in Secondary Endpoint 1).

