#### **6.5 Duration of Study Participation**

The study duration will be approximately 12 months. The duration of study participation for each individual participant will be 1 month, including screening/index visit, study intervention and follow-up. We will target 1 study enrollee per week, with a goal of 2 per week, and expect to enroll participants within an 11-month period. The study will end approximately one month after the final participant is enrolled, at the conclusion of that participant's one-month follow up. We know from our previous and ongoing studies that recruitment should not be limited by the number of eligible patients.

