#### **6.7 Participant Withdrawal or Termination**

##### **6.7.1 Reasons for Withdrawal or Termination**

Participants are free to withdraw from participation in the study at any time upon request. An investigator may terminate participation in the study if:

- After the first 8 mg dose of BUP is administered, a study participant experiences any clinical AE (e.g., allergic reaction) that would preclude safe administration of the subsequent BUP 24mg dose during the index visit. The initial BUP 8mg is a standard dose used in the ED; it is only the subsequent BUP 24mg (for a total dose of BUP 32mg) that is being evaluated in this study.
- Thus, if a participant develops a reaction to the initial 8mg dose, the reaction would be attributed to the standard dose of BUP and not the larger dose of being tested.
- The participant meets an exclusion criterion (either newly developed or not previously

Study Number: s19-01700

Version: 7.0

Version Date: 08/01/2022

recognized) that precludes further study participation.

- The participant becomes a prisoner.

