## **8.3 Time Period and Frequency for Event Assessment and Follow-Up**

The occurrence of an AE or SAE may come to the attention of study personnel during study visits and interviews of a study participant presenting for medical care, or upon review by a study monitor. All AEs including local and systemic reactions not meeting the criteria for SAEs will be captured on the appropriate RF. Information to be collected includes event description, time of onset, clinician's assessment of severity, relationship to study product (assessed only by those with the training and authority to make a diagnosis), and time of resolution/stabilization of the event. All AEs occurring while on study must be documented appropriately regardless of relationship. All AEs will be followed to adequate resolution.

Any medical condition that is present at the time that the participant is screened will be considered as baseline and not reported as an AE. However, if the study participant's condition deteriorates at any time during the study, it will be recorded as an AE. UPs will be recorded in the data collection system throughout the study.

Changes in the severity of an AE will be documented to allow an assessment of the duration of the event at each level of severity to be performed. AEs characterized as intermittent require documentation of onset and duration of each episode.

The PI will record all reportable events with start dates occurring any time after informed consent is obtained until 7 (for non-serious AEs) or 30 days (for SAEs) after the last day of study participation. At each study visit, the investigator will inquire about the occurrence of AE/SAEs since the last visit. Events will be followed for outcome information until resolution or stabilization.

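### Participants who stop after a first-dose adverse event are withdrawn from the study, not only from dosing, and so have no scheduled safety or outcome assessment after the index visit

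*Combined protocol and SAP*

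**What the plan says.** All references are to the combined protocol and SAP.

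- **The rule in the visit schedule (Section 7.4.2).** After a qualifying event following the first dose, "the second dose will not be given and the participant will be withdrawn from the study without receiving subsequent doses". Qualifying events are illustrated by allergic reaction and by the clinically significant events listed in Section 5.1.1.
- **The rule in the risk section (Section 2.1.4).** If an event after the initial dose precludes further dosing, "the subsequent dose will not be administered and the patient will be withdrawn from the study". The same section says that precipitated withdrawal would not automatically rule out the next dose and is decided case by case.
- **The protections section (Section 2.1.6).** Individuals whose event compromises safe participation "will be discontinued from further medication administration (as described in medication risks) and provided referrals for other treatment or to specialized care".
- **The withdrawal section (Section 6.7.1).** The wording is permissive: "An investigator may terminate participation in the study if" one of several conditions holds, the first being an event after 8 mg that precludes the 24 mg dose.
- **How events are found.** Section 5.1.2, item 2: "Adverse events will be assessed using an adverse events checklist to be completed at the conclusion of the index visit and at each study visit". Sections 7.4.3.1, 7.4.4 and 8.4.1 place detection after discharge at the Day 1-3 visits and the Day 30 call.
- **How long events are recorded (Section 8.3).** New events are recorded from consent "until 7 (for non-serious AEs) or 30 days (for SAEs) after the last day of study participation". The protocol does not define that last day.
- **What continues after removal.** Section 6.7.2 provides monitoring and treatment, in the ED or as an outpatient, for those removed because of an adverse event. Section 8.3 follows known events to resolution and has the sponsor notified of possibly related events at any time after termination. Section 6.7.2 also continues enrollment towards 35 when participants are withdrawn.

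**The concern.** Stopping the study drug and leaving the study are different things, and the plan treats the first as if it entailed the second. The people removed are those who had an adverse event on the first part of the regimen, and it is their later course that a safety study most needs to observe. Section 2.1.6 names close follow-up and assessment within the study as one of the measures that reduce physical risk. The withdrawal rule takes that measure away from this group.

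Two things are at stake. One is capture of new events in the days after discharge. The other is interpretation of the 30-day tables on engagement, drug use, overdose and healthcare use (Section 5.1.2, item 5): if those who reacted leave and enrollment continues, the tables describe people who tolerated 8 mg, without saying so. Safety is one of the four elements of the first overarching objective (Section 3), so this matters even in a descriptive pilot.

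**Working it through.** The plan gives no figure on this point to reproduce. The check is a reading of the rules, a count of contacts and simple window arithmetic.

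**1. Which rule operates?** Sections 2.1.4 and 7.4.2 both say the participant will be withdrawn from the study. Section 6.7.1 says the investigator may end participation. Section 2.1.6 mentions only stopping medication and referral, but it refers back to the medication-risks text, which is Section 2.1.4. The operative instruction is therefore withdrawal from the study, with unresolved doubt over whether it is mandatory or discretionary.

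**2. Scheduled adverse-event assessments after the index visit** (Sections 1.1.1, 7.4.3.1, 7.4.4).
- Participant who stays in: Days 1, 2 and 3 plus Day 30 = 3 + 1 = 4.
- Participant withdrawn at the index visit: 0.

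**3. What is lost and what is kept.**
- Kept: follow-up of the known event, clinical monitoring and treatment, and notification of possibly related later events (Sections 6.7.2 and 8.3). None of these sets a contact schedule, so a new event is found only if someone volunteers it.
- Lost: the checklist for new events, the overdose and substance-use measures, and Day 30 engagement.

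**4. Recording windows (Section 8.3).** End of window = last day of participation + 7 (non-serious) or + 30 (serious).
- Completer, Day 30: 30 + 7 = Day 37 and 30 + 30 = Day 60. With the ±3-day tolerance on the call, the ranges are Days 34-40 and 57-63.
- Withdrawn at the index visit, *assuming* that day is the last day of participation: 0 + 7 = Day 7 and 0 + 30 = Day 30.
- Difference under that assumption: 30 days on each window (27-33).
- If instead the last day is taken from the one-month participation stated in Section 6.5, the windows coincide and the difference is 0.

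The gap is thus anywhere from 0 to about 30 days, depending on a term the protocol leaves open. The 0-versus-4 count in step 2 does not depend on it.

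**5. How many people?** The documents give no number. For illustration only, take 1, 3 or 5 affected.
- Out of 35 enrolled: 1/35 = 2.9%, 3/35 = 8.6%, 5/35 = 14.3%.
- If each is replaced: 1/36 = 2.8%, 3/38 = 7.9%, 5/40 = 12.5% of all those started on the regimen.

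**6. Precipitated withdrawal.** Section 7.4.2 points to the Section 5.1.1 list, which includes severe precipitated withdrawal, and attaches study withdrawal to events on it. Section 2.1.4 leaves further dosing after precipitated withdrawal to the study clinician. Read literally, one participant could fall under both instructions, and how this is resolved changes how many leave the study.

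**The case against.** The strongest defence is in Section 6.7.1. The initial 8 mg is a standard ED dose, only the added 24 mg is under evaluation, and a reaction to the first dose is attributed to standard treatment. Section 3.1 frames the primary objective among those who receive 32 mg, and the duration-of-effect objective cannot be informed by someone who received 8 mg. On this view, following only those who completed loading is a declared choice. The sponsor could add that over-sedation and precipitated withdrawal are expected within 30 to 90 minutes (Section 2.1.4), that the triggering event is followed to resolution, that the one ED chart review described (94 patients, Section 2.1.3) reported no adverse events, and that all analyses are descriptive (Section 10.1), so no planned comparison is biased.

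Much of this stands. Participants who stop at 8 mg do not belong in the duration-of-effect analysis of 32 mg, the number affected may be small or zero, and the primary endpoint is unaffected by follow-up. The attribution argument does not justify ending collection, however. Section 8.3 requires all adverse events to be documented whatever their relationship to treatment, and Section 6.9.4 makes the 8 mg part of the strategy under study.

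A reader might infer three stronger points that the documents do not support:
- *Section 2.1.6 contradicts Sections 2.1.4 and 7.4.2.* Its reference back to the medication risks makes it compatible with them.
- *Those who react receive the least safety follow-up overall.* The known event has open-ended follow-up and possibly related later events stay reportable. Only scheduled collection of new events and outcomes is reduced.
- *The windows are certainly Day 7 and Day 30 against Day 37 and Day 60.* That rests on an undefined term.

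**Conclusion.** The point holds in a limited form and is worth correcting. As written, a participant with a qualifying first-dose event leaves the study and has 0 scheduled adverse-event assessments after the index visit instead of 4. New events and 30-day outcomes are then not actively collected in this group, and with enrollment continuing to 35 the follow-up data are selected for tolerance of the first dose.

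The count assumes that withdrawal takes effect at the index visit and that withdrawn participants do not attend study visits. The window difference (0 to about 30 days) and the share affected are conditional, as the working shows; the percentages are not forecasts.

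A reader might also conclude that the stated serious-event window should be cut back to the Day 30 contact, because Section 6.5 says "The study will end approximately one month after the final participant is enrolled, at the conclusion of that participant's one-month follow up" and the windows run beyond it. The documents do not require that. Section 8.3 already has participants instructed at the last visit to report later related events, and a shorter window would reduce the stated coverage for completers.

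**What to change.** 1. In Sections 2.1.4, 6.7.1 and 7.4.2, separate stopping study drug from leaving the study, and use the same wording, mandatory or discretionary, in all three.
2. Keep participants who stop dosing because of an adverse event in the Day 1-3 and Day 30 safety and outcome assessments unless they withdraw consent. This concerns assessments only. The sponsor should state separately how the prescription attached to the Day 1-3 visits applies to them; no rule is proposed here. Section 8.4.4 offers a precedent: participants who become pregnant stay in the study although pregnancy bars entry.
3. In the safety and 30-day tables, report these participants and identify them by dose received. Analyses of the duration of effect of 32 mg can remain restricted to those who received it.
4. In Section 8.3, define the last day of participation so that participants who stop dosing have the same recording windows as completers, without shortening the stated serious-event window.
5. Reconcile Section 2.1.4 with Section 7.4.2 (through the list in Section 5.1.1) on precipitated withdrawal after the first dose. Which clinical rule applies is for the sponsor.

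Cost: protocol wording, a few extra visits, and follow-up payments of up to 3 × $40 + $40 = $160 per affected participant (Section 15.3), plus the travel support already offered. The documents do not show whether the extra visits are within the existing budget.
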